5.4.2 Masking Procedures

All personnel who have contact with the child and caregiver will be blinded to participant group assignment except for personnel on the Data & Statistics Team. In order to maintain blinding, the dental examiners will not have access to study arm allocation.

5.5 Subject Withdrawal

5.5.1 Reasons for Withdrawal

Subjects are free to withdraw from participation in the study at any time upon request.

Subjects who drop out (or withdraw) from the study by their own choice will be considered dropouts/withdraws.

An investigator may terminate a study subject's participation in the study if:

- Any medical condition or situation occurs such that continued participation in the study would not be in the best interest of the subject.
- The child transfers out of the school district) that precludes further study participation.

5.5.2 *Participants who are discontinued from the study by one of the study personnel will be considered a discontinuer. Handling of Subject Withdrawals or Subject Discontinuation of Study Intervention*

All reasons for dropout/withdrawal or discontinuation of the study intervention will be documented in the tracking database and reviewed by the study team and **reported to the NIDCR Medical Monitor**. For gathering information on discontinuation, **Outreach Workers** will be contacting subjects at the 2 follow-up time points (2 weeks after initial dental screening and 2 weeks before the last dental screening).

In the event of a subject telling the **Outreach Worker** that he/she is dropping out of the study, the **Outreach Worker** should gather the following information as much as the subject allows.

- Record the reason for dropping out of the study.
- Record any event reported by subjects that the PI determines to be an unanticipated problem.
- Debrief about the intervention.
- Complete the appropriate questionnaire nearest the drop out time point.

If it is determined by study personnel that a participant should be discontinued from the study, the decision to withdraw a participant must be discussed and confirmed by the **PI** and **Clinical Site Investigator**. If both agree that a subject should be withdrawn from the study, the date of withdrawal and reason(s) for withdrawal should be recorded in the tracking database.

5.6 Premature Termination or Suspension of Study

Termination of the study normally would occur at the end of subject accrual and completion of all study procedures. For various reasons a study may terminate prematurely. Written notification, documenting the reason for study suspension or termination, will be provided by the suspending or terminating party to the Principal Investigator (PI) , Medical Monitor, or NIDCR. If the study is prematurely terminated or suspended, the PI will promptly inform the IRB and will provide the reason(s) for the termination or suspension.

Circumstances that may warrant termination include, but are not limited to:

- Determination of unexpected, significant, or unacceptable risk to subjects.
- Insufficient adherence to protocol requirements.
- Data which are not sufficiently complete and/or evaluable.
- Determination of futility.

6 STUDY INTERVENTION

6.1 Study Behavioral or Social Intervention(s) Description

The new referral intervention letters (Arms 1 to 4) have been based on the CSM theory. Expert input was sought from both CSM experts and other Health Behavior Theory (HBT) experts to assess the consistency of the letter text to the CSM theory. All experts agreed that the new referral text is consistent with the CSM theory. But, the text may not be specific and other theories especially the Health Belief Model (HBM) and Theory of Planned Behavior (TPB) could also be mapping to the letter text. Two ways in which we propose to address this in our study: is to include additional theory-based measures as potential mediators (caregiver beliefs and attitudes, self-efficacy, subjective norms) of the intervention's effects; another way is to report the results of this study where other alternative theories are discussed. The modified standard letter (control) does not map to any HBT constructs.

Arm 1: The intervention is the CSM referral letter alone (English and Spanish; MOP Appendices section 6). The letter text includes the cognitive dimensions of the CSM (identity, cause, timeline, consequences and controllability). Table 6.1.1 gives the letter text and the CSM cognitive constructs that the text maps to. The letter has been tested for readability and clarity with caregivers of K-2 children. The Spanish translation was done by a native Mexican Spanish speaker and back translated by a second individual to ensure comparability. Both versions were written at a 6th grade level or lower. The letter will be sent home with the child on the day of screening and mailed to the caregiver address within 24 hours. School District records include information on the primary language spoken at home. The address will be obtained during recruitment and verified with the school secretary.

Arm 2: The intervention is the CSM referral letter + the dental information guide (DIG; MOP Appendices Section 6) to reinforce/change illness perception, knowledge about dental caries, and resources to seek care. The dental information guide is a brochure with illustrations which provides myths and facts about dental caries, hints for getting dental care, making appointments and Medicaid access, transportation and dentist availability resources. The information guide was pilot-tested and modified based on caregivers and community leaders input. While the general information on dental caries is similar for both sites, other resource information on how to seek care and a list of dentists is adapted to the specific site (see MOP Appendices Section 6 for site-specific DIG). As with the other arms, the letter will be sent home with the child on the day of the screening and mailed to the caregiver's address within 24 hours.

Arm 3: The intervention is the reduced (removing text corresponding to "timeline") CSM referral letter alone (English and Spanish; MOP Appendices Section 6). The letter includes the remaining cognitive dimensions of the CSM (identity, cause, consequences and controllability). While the last line (timeline construct) reinforces the core issues (baby teeth's impact on adult teeth and the disease's chronic nature), the text and constructs leading up to the last line is equally important. We think that this final message is fundamental to the intervention letter and this version will allow an estimate of the effect of the "timeline" text itself. The letter has been tested for readability and clarity with caregivers of K-2 children. The Spanish translation was done by a native Mexican

Spanish speaker and back translated by a second individual to ensure comparability. Both versions were written at a 6th grade level or lower.

Arm 4: The intervention is the reduced CSM referral letter + reduced dental information guide (Reduced DIG; MOP Appendices Section 6) to reinforce/change illness perception, knowledge about dental caries, and resources to seek care. The reduced dental information guide is a brochure with illustrations that provides myths and facts about dental caries, hints for getting dental care, making appointments and Medicaid access, transportation and dentist availability resources. As with the reduced letter, text and illustrations related to the “timeline” construct have been removed in the reduced dental information guide. This version will allow for an estimate of the effect of the “timeline” text and illustrations. While the general information on dental caries is similar for both sites, other resource information on how to seek care and a list of dentists is adapted to the specific site (see MOP Appendices Section 6 for site-specific DIG). The letter will be sent home with the child on the day of the screening and mailed to the caregiver’s address within 24 hours.

Arm 5: The control is the modified standard referral letter (based on November 2007 guidelines for Oral Health Screening in Ohio Schools. MOP Appendices Section 6). This letter is consistent with others used across the country. Both Ohio and Washington sites will use the same standard letter. As with Arms 1, 2, 3 and 4, the letter will be sent home with the child on the day of the screening and mailed to the caregiver’s address within 24 hours.

Table 6.1.1 Text of intervention letter and associated CSM constructs

Intervention letter text	CSM construct
Cavities are the #1 childhood health problem . Children may have cavities even if they do not have pain . Cavities should be treated when found.	Identity
Cavities can be serious in baby teeth. Cavities can affect children’s learning and how they look and feel about themselves .	Consequences
Other health problems may not be under your control. But, you can prevent cavities by taking your child to the dentist at least once a year . Your child will benefit from this greatly.	Controllability
Cavities do not just happen. Bacteria cause cavities. A dentist can clear up the bacteria.	Causes
If cavities are not treated, the bacteria in baby teeth can affect adult teeth .	Timeline

6.2 Administration of Intervention

The referral letter (and dental information guide for Arms 2 and 4) will be sent home with the child on the day of screening and mailed to the caregiver's address within 24 hours. School District records include information on the primary language spoken at home. The address will be obtained during recruitment and verified with the school secretary.

Procedures will be in place to make certain that the referral letters are received. In the R34 pilot study, caregivers preferred to have it mailed. But when the letter was sent home both with the child and also mailed to the caregiver, 75% received the letter either through child or mail or both, while 25% reported they did not receive the letter. To maximize the chance the referral letter and/or information guide are received, a trained Outreach Worker will call the caregiver within 2 days to clarify the receipt: 5 attempts will be made at various times during the day and evening. If the letter was not received, the worker will verify the address and another packet will be sent. The training procedure for the Outreach Workers is in the next section and a more detailed account is in the MOP (Refer to Section 6). In Washington some Outreach workers will be bi-lingual.

6.3 Procedures for Training Interventionists and Monitoring Intervention Fidelity

The **Project Coordinator** in Cleveland and Washington will be responsible for facilitating the caregiver participants' access to the interventions. Given that the nature of the interventions (i.e., referral letters), are structured, the **Project Coordinator** will primarily be responsible for assuring that the letters are sent. **Outreach workers** will be responsible for assuring that letters are received by the caregiver. They will not be personally delivering the intervention information. This makes training and fidelity assessment less complicated. This section generally describes the procedures for training the **Outreach Workers** and monitoring compliance with study procedures (See MOP Section 5.2 for a detailed description).

Project Coordinators will supervise the **Outreach Workers** at their respective sites. Staff training for **Project Coordinators** (Ohio and Washington), and **Outreach Workers** (Ohio only), will be centrally conducted at Case Western Reserve University (CWRU). The Washington **Project Coordinator** will receive training at CWRU and in turn will train the outreach staff at Washington. While the curriculum varies depending on the staff member's role in the project, at a minimum all staff will be trained in the topics of **Human Subject Protection, Good Clinical Practice (GCP), and Protocol training**.

Intervention fidelity ensures that the intervention was conducted as planned, i.e., follows the study protocol. The importance of adhering to the study protocol (e.g., when to send out referral letters, when to make phone calls and following the phone call scripts) will be emphasized during the **Outreach Worker** training as well as following the MOP. One aspect of **Outreach Workers'** duties will require them to make phone calls to caregiver participants confirming receipt of the letters. To ensure that **Outreach Workers** make a similar number of phone calls and provide the same information to each participant the calls will be recorded. The **Project Coordinator** in each respective site will listen to each of the first 10 calls (reminder calls to return the questionnaire). **Outreach Workers** will receive additional training if there are deviations from the script; then.

Then, the first ten (10) of the following remaining type of calls will be recorded and reviewed for each Outreach Worker (confirmation of receipt of referral letters-call #2, and reminders to return completed questionnaires-calls #4 and #6) to assure continued fidelity. Furthermore, all contacts with caregivers will be entered into the tracking database and reviewed to ensure that **Outreach Workers** are following the protocol/MOP.

6.4 Assessment of Subject Compliance with Study Intervention

Procedures will be in place to make certain that the referral letters (and DIG) are received/read/understood. .

The following procedures will maximize the chance that caregivers receive the referral letter (and DIG for Arms 2 and 4):

- Include the same generic code (ex. 1001) at the bottom of all referral letters.
- A trained Outreach worker (OW) will call the caregiver within 48 hours of the dental screening to confirm receipt of the referral letter: 5 attempts will be made at various times during the day and evening.
- When calling to confirm receipt of the referral letter, the Outreach worker will ask the caregiver to read the code at the bottom of the letter.
- If the referral letter was not received, the Outreach worker will verify the caregiver's address and send another one with her/his child or by mail, depending on the caregiver's preference.
- The training procedures for the Outreach workers are described in the next section and a more detailed account can be found in the MOP (Refer to Section 6). In Washington some Outreach workers will be bi-lingual

In addition, to ensure that caregivers read and understood the referral letter, a self-addressed stamped postcard will be enclosed with the referral letter. There will be two questions on the postcard: (a) I have read and understood the letter (yes/no); (b) I understand that my child's dental screening in the school was not a complete dental exam (yes/no). Caregivers will be able to answer question (b) if they read the letter because this sentence is in both the standard and CSM referral letters. Outreach workers will remind caregivers to answer the questions and return the postcard.

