Confounders	Child's age, race, dental visit Caregiver socio-demographics (age, race, SES, education, marital status)	Baseline	NHANES IV
Subject compliance with Intervention	
 • Whether the referral letter (and DIG) was received (generic code) • Whether the referral letter (and DIG) was read/understood (Postcard) 	Within 2 days after Baseline dental exam	

1. **Baseline:** prior to screening dental exam; **At randomization:** after baseline dental screening exam; **Two-weeks:** Two weeks after randomization; **Exit:** two weeks before end of school year dental exam

2. Caregiver self-efficacy and subjective norms will also be considered as potential **mediators** in the additional mediational analyses, and will be measured at the **Exit** in addition to **Baseline**.

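### Receipt and reading of the Dental Information Guide are listed as measured, but the code, call and postcard in Section 6.4 cover only the letter

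*Combined protocol and SAP*

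**What the plan says.** Table 3.2.1 (Section 3.2.2) lists two compliance measures: "Whether the referral letter (and DIG) was received (generic code" and "Whether the referral letter (and DIG) was read/understood (Postcard". Section 6.4 opens with the same aim: "Procedures will be in place to make certain that the referral letters (and DIG) are received/read/understood".

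The steps that follow in Section 6.4 are narrower:

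- Code: "Include the same generic code (ex. 1001) at the bottom of all referral letters".
- Call: "the Outreach worker will ask the caregiver to read the code at the bottom of the letter".
- Resend: "If the referral letter was not received, the Outreach worker will verify the caregiver's address and send another one".
- Postcard: two questions. The first is "a) I have read and understood the letter (yes/no". The second tests a sentence that the protocol says appears in both the standard and the CSM letters.

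Section 6.2 is wider in places. It gives delivery of the guide as part of the purpose of the call, and its resend rule reads "If the letter was not received, the worker will verify the address and another packet will be sent". Section 7.2 likewise speaks of confirming and resending packets. Section 5.4.2 keeps everyone in contact with families blinded, apart from the Data & Statistics Team.

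**The concern.** The guide is the only planned difference between Arm 1 (CSM letter) and Arm 2 (CSM letter plus DIG). That comparison is one of the three named in Section 12.2. The plan intends to document whether the guide was received and read, but the instruments it names for this cannot produce the information.

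An Arm 2 caregiver who holds the letter but not the brochure can read out the code and truthfully answer both postcard questions. That caregiver counts as fully compliant, although the material received is that of Arm 1. If Arm 1 and Arm 2 turn out alike, the trial team would have no direct way to tell a guide that did not work from one that was not delivered or not read. Arm 4 has the same gap with its reduced guide.

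**Working it through.** **Step 1. Set the promise against the instrument.**

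| Listed measure | Named instrument | What the instrument covers |
|---|---|---|
| Letter and DIG received | Generic code | Code printed on the letter; caller asks for the letter's code |
| Letter and DIG read or understood | Postcard | One question on the letter; one on a sentence in the letters |

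No step in Section 6.4 asks about the guide.

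**Step 2. Trace the cases in Arm 2 or Arm 4.**

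- Letter and guide both missing: the call finds no letter. Sections 6.2 and 7.2 send a new packet, which on its natural reading includes the guide. This case is covered.
- Letter present, guide missing: the code is read out, and the resend condition in both 6.2 and 6.4 (letter not received) is not met. The loss is not recorded and the guide is not replaced.
- Both present, guide unread: the postcard records only whether the letter was read. The loss is not recorded.

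**Step 3. Reproduce the planned power for Arm 1 versus Arm 2.**

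Inputs from Sections 12.2 and 12.4: rates 37% and 57%, two-sided pooled Z test, alpha 0.05, 102 per arm per site, 204 per arm combined.

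Power = Φ{[d − 1.96·√(2p̄(1−p̄)/n)] / √[(p₁(1−p₁)+p₂(1−p₂))/n]}, with d = p₂ − p₁ and p̄ their mean.

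With d = 0.20 and p̄ = 0.47:

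- n = 102: (0.2000 − 0.1370)/0.0685 = 0.92, so power is 82.1%.
- n = 204: (0.2000 − 0.0969)/0.0484 = 2.13, so power is 98.3%.

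The plan states 80% and 98%. The combined figure agrees. The per-site figure agrees once the plan's 5% transfers are allowed for: 102 × 0.95 = 96.9 per arm gives 80.1%. The planned sample size is sound.

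**Step 4. Illustrate the effect of missing guides.**

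Assumption: a share f of Arm 2 has the letter but not the guide and responds at the Arm 1 rate. The Arm 2 rate is then 0.57(1−f) + 0.37f = 0.57 − 0.20f.

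| f (assumed) | Arm 2 rate | Power per site (102/arm) | Power combined (204/arm) |
|---|---|---|---|
| 0 | 57% | 82.1% | 98.3% |
| 5% | 56% | 78.1% | 97.3% |
| 10% | 55% | 73.6% | 95.7% |
| 15% | 54% | 68.6% | 93.5% |
| 20% | 53% | 63.4% | 90.4% |
| 25% | 52% | 57.8% | 86.5% |

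Arm 5 versus Arm 2, the first test in the gatekeeping sequence, keeps over 99.9% power even at f = 25%. Any loss would therefore show in Arm 1 versus Arm 2.

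**The case against.** Several points on the other side stand.

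- A reader might infer that a missing guide is never found or replaced. Sections 6.2 and 7.2 do not support that: a guide lost with its letter comes back with the new packet, and materials already go out twice, with the child and by mail. Beside 7.2, the difference between the resend wording in 6.2 and 6.4 looks like loose drafting.
- A reader might infer that the contrast is in fact diluted, perhaps by up to 25%. The documents give no rate of letter without guide. The pilot's 25% in Section 6.2 is non-receipt of the letter, which is a different event and the one the call is built to catch. It neither estimates nor bounds f.
- A reader might infer that the primary test is compromised. It is not. Failing to measure receipt does not reduce power, the as-randomised comparison stays valid, and Section 12.4 uses no compliance variable. Site-level tests run only after the overall test succeeds, so the combined column is the more relevant one.
- A reader might fault the shared code for letting a wrong-arm packet pass. Nothing says the code was meant to verify arm, and one code with letter-only questions fits the blinding of callers.
- The questionnaires give some indirect evidence: which items helped (2-week question 1.5; final question 5.5 in part 5A) and which group the caregiver believes they were in (final questions 5.7 and 5.5 in parts 5A and 5B). But the 2-week helped item goes only to those who visited or booked, and none of these asks about receipt or reading.
- The call scripts are in the Manual of Procedures, which is not available here and might mention enclosures. The protocol itself, however, specifies the two postcard questions and the letter code, and it states that supplemental materials are not part of it.

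None of this closes the mismatch between Table 3.2.1 and Section 6.4.

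**Conclusion.** The point holds as a measurement gap. The protocol lists DIG receipt and reading as assessed, and the instruments it names assess only the letter. What is lost is the ability to describe exposure in Arms 2 and 4 and to interpret a null Arm 1 versus Arm 2 result.

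The size of any attenuation is unknown. The power figures depend on an assumed f of 5% to 25%, on caregivers without the guide responding at exactly the Arm 1 rate, and on the 57% planning rate describing full exposure. That rate is self-reported and counts appointments, so some incomplete exposure may already be in it. The gap deserves correction whatever the true rate, because the correction is cheap and concerns the only component separating two of the main arms.

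**What to change.** 1. Add one neutral item to the existing postcard, identical in all five arms and not naming the guide, for example: list each item in your packet and whether you read it. Naming the guide would tell Arms 1, 3 and 5 that one exists.
2. Return the postcards to the Data & Statistics Team, so that callers stay blinded.
3. Have that team compare the listed items with the assigned packet and trigger a resend of the full assigned packet when any item is missing. Record DIG status as unknown, not as received, where no postcard comes back.
4. Make Table 3.2.1 and Sections 6.2, 6.4 and 7.2 agree on what is checked, what triggers a resend and what is resent.

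A packet number read out by telephone is not a good substitute. If it is printed on every item, the letter alone passes the check. If the caller asks for the last page, the caregiver may mention a brochure to blinded staff.

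The cost is one more postcard item, a small amount of tracking by the data team and a short amendment, with no extra staff or visits. Postcard return will be incomplete, so the measure will be partial. If the team prefers not to collect it, removing the guide from the compliance rows of Table 3.2.1 and from the aim of Section 6.4 would end the contradiction but leave exposure unknown.
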